1.4 Rational for Targeted Dose

A concern regarding the use of Everolimus in oncology is the potential for immunosuppression during treatment. Consequently, in addition to individualizing the Everolimus dose according to the patient's body surface area, this protocol requires the upward titration of the dose from 4.5 mg/m², subject to tolerability, with the objective of achieving trough Everolimus levels in the range of 5-15 ng/mL. This range is based on the Phase II data from a TSC study conducted at the Cincinnati Children's Hospital Medical Center.²⁴ In this study, patients were treated with Everolimus from a starting dose of 3 mg/m² with subsequent upward titration to attain a RAD001 trough in the range 5-15 ng/mL. This regimen was efficacious (35% of patients had >50% shrinkage at 6 months) and showed acceptable tolerability. The starting dose of 4.5 mg/m² is based upon separate data from a phase I pediatric oncology study concluded that the maximum tolerated dose of everolimus in children is 5 mg/m²/day.²⁵ In order to optimize patient safety, and to ensure that excessive exposure does not occur, trough concentrations will be assessed initially and monitored as appropriate throughout the study.

Pharmacokinetics of RAD001 in patients with TSC:

During Study RAD001M2301, in patients with TSC who have SEGA, pre-dose (C_{min}) and 2-hour post-dose (C_{2h}) PK blood samples were collected at steady-state. Ages of patients in the Everolimus arm of study ranged from 1 to 23.9 years. Patients in this study received a starting dose of 4.5 mg/m²/day which was subsequently titrated to a whole blood trough concentration of 5-15 ng/mL. This is the starting dose and trough range approved for this indication.

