4.0 TREATMENT PLAN

4.1 Treatment Dosage and Administration

The investigational treatment is Everolimus; it will be administered in conjunction with best supportive care. Best supportive care includes all care provided to patients deemed necessary by the treating physician, such as analgesics and anti-diarrheal therapies.

- Everolimus will be administered by mouth at a starting dose of 4.5 mg/m²/day. Each course of therapy will last for 28 days for up to 24 courses.
- The starting dose 4.5 mg/m² of Everolimus will be titrated upward (or downward), subject to tolerability, with the objective of achieving trough Everolimus levels in the range of 5-15 ng/mL.
- All dosages prescribed and dispensed to the patient and all dose changes during the study must be recorded.
- Medication labels will comply with US legal requirements and be printed in English. Additional labels may be used in the primary language of the study participant. They will supply no information about the patient. The storage conditions for Everolimus will be described on the medication label.

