4.5.1 Dose modification and dose delay

4.5.1.1 Therapeutic drug monitoring: Therapeutic drug monitoring of Everolimus blood concentrations is required for patients enrolled on study and taking Everolimus. Testing is to be performed by Quest Diagnostics using a validated bioanalytical LC/MS method (test code 18883X). Trough concentrations should be assessed 2 weeks (+/- 4 days) after the initial dose, after any change in dose or formulation, after an initiation or change in co-administration of CYP3A4 inducers or inhibitors, or after any change in hepatic status.

4.5.1.2 Dosing modifications:

Titrate the dose to attain trough concentrations of 5 to 15 ng/mL.

- For trough concentrations less than 5 ng/mL, increase the daily dose by 2 mg and repeat trough concentration in 2 weeks (+/- 4 days).
- For trough concentrations greater than 15 ng/mL, reduce the daily dose by 2 mg and repeat trough concentration in 2 weeks (+/- 4 days).
- The lowest possible dose level of Everolimus is 2 mg daily.
- If dose reduction is required for patients receiving the lowest available strength, administer every other day.

- For patients who do not tolerate the protocol-specified dosing schedule, dose adjustments are permitted in order to allow the patient to continue the study treatment. Dose levels are as follows: Level -2 = 3 mg/m²/dose, Level -1 = 3.8 mg/m²/dose, Level 0 = 4.5 mg/m²/dose, Level +1 = 5.2 mg/m²/dose and Level +2 = 6 mg/m²/dose. If dose adjustments need to be made for toxicity, patients' doses of Everolimus should not be targeted to achieve a trough level of 5 – 15 ng/mL.

Table 4-1**Dosing guidelines for Everolimus-related non-hematologic toxicities**

Toxicity	Action
Non-Infectious Pneumonitis	Please refer to Table 4-3.
Reactivation of HBV or HCV flare	Please refer to Table 4-5.
AST or ALT elevation	Maintain current dose level
Grade 1 (> ULN - 3.0 x ULN)	
Grade 2 (> 3.0 - 5.0 x ULN)	
AST or ALT elevation Grade 3 (> 5.0 - 20.0 ULN)*	Interrupt Everolimus administration until resolution to ≤ grade 1 (or ≤ grade 2 if baseline values were within the range of grade 2). If resolution occurs ≤ 7 days, Everolimus should be re-started at the dose level prior to interruption. If resolution takes > 7 days, or if event recurs within 28 days, hold Everolimus until recovery to ≤ grade 1 or baseline grade / value and reintroduce Everolimus at one dose level lower, if available.

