- Everolimus trough levels will be assessed 2 weeks (+/- 4 days) after starting drug. If the level is outside of the target range, then the dose should be adjusted to achieve a trough level of 5 – 15 ng/ml. Trough levels should be assessed within one hour before taking the daily dose.
- Whenever any dose adjustment of Everolimus occurs, trough levels should be reassessed two weeks (+/- 4 days) following the adjustment to ensure that the new dose achieves the target drug trough level of 5-15 ng/ml.
- Furthermore, Everolimus trough levels should be assessed 2 weeks (+/- 4 days) following the starting, ending, or changing of the dose of inducers or inhibitors of CYP3A4 or P-glycoprotein.

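### Sections 4.5.1.2 and 5.2.4 disagree on whether a dose changed for toxicity is still steered to a 5–15 ng/mL trough; two related dosing rules also need reconciling

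*Combined protocol and SAP*

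**What the plan says.** **Trough targeting.** Section 4.1 has the starting dose of 4.5 mg/m² "titrated upward (or downward), subject to tolerability", aiming at a trough of 5–15 ng/mL; section 1.4 carries the same qualifier. Section 4.5.1.2 gives the step for a trough below 5 ng/mL: "increase the daily dose by 2 mg and repeat trough concentration in 2 weeks". It gives the mirror-image 2 mg reduction above 15 ng/mL. The same section lists dose levels for patients who do not tolerate the schedule, including "Level -1 = 3.8 mg/m²/dose, Level 0 = 4.5 mg/m²/dose", and ends by saying that after an adjustment for toxicity patients' "doses of Everolimus should not be targeted to achieve a trough level of" 5–15 ng/mL.

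Section 5.2.4 reads differently. On timing it says "Whenever any dose adjustment of Everolimus occurs, trough levels should be reassessed two weeks", with a window of four days either side. The stated aim of that recheck is that the changed dose should bring the patient into the target range, and no group of patients is excepted. Section 5.2.1 and footnote 9 of Appendix II refer the reader to 5.2.4 for trough testing after a dose adjustment.

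**Floor.** Section 4.5.1.2 sets 2 mg daily as the lowest dose level and directs alternate-day dosing when a patient on the lowest strength needs a reduction. The recurrence rows of Table 4-1 (intolerable grade 2 mucositis or a grade 3 event after a reduction) and Table 4-2 (grade 3 toxicity after a reduction) say the drug must be stopped below 2 mg daily.

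**Step size.** Section 4.6.2, on CYP3A4 and P-glycoprotein interactions, uses the same cut-offs of 5 and 15 ng/mL but changes the dose by +33% or -25%. For strong inducers it also calls for an increase of one increment after 7 days, without giving the size of an increment.

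**The concern.** A reduction made for toxicity is a dose adjustment, so both 4.5.1.2 and 5.2.4 apply to it. One says the reduced dose is not to be aimed at the trough range; the other says the recheck is there to make sure it reaches that range. A site working from the schedule of events is sent to the second text and meets no exception there.

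The main stake is patient safety: two sites could manage the same child differently after a toxicity reduction, and one of them could raise the dose again. It also leaves the dosing strategy under test in an 18-patient trial without a single definition.

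At the floor, one text can be read as keeping a child on drug and another as stopping it for good. Permanent discontinuation is the event counted by the stopping rule in section 7.6. The step-size overlap is smaller: for a child on an interacting drug, the plan does not say which of two steps follows an out-of-range trough.

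**Working it through.** **1. The two texts side by side, for a child whose dose has just been reduced for toxicity**

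| Question | 4.5.1.2 | 5.2.4 |
|---|---|---|
| Does it cover this child? | Yes, by name (adjustment for toxicity) | Yes (any adjustment) |
| Is the trough rechecked? | Yes, through 4.5.1.1 (any change in dose) | Yes, at two weeks |
| Is the dose aimed at 5–15 ng/mL? | No | Yes |
| Exception or cross-reference? | None to 5.2.4 | None to 4.5.1.2 |

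Testing is not in dispute; its purpose is.

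**2. Size of one trough step against one toxicity reduction**

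Inputs from 4.5.1.2: Level 0 = 4.5 mg/m², Level -1 = 3.8 mg/m², low-trough step = +2 mg. Body surface area (BSA) is not in the documents, which give only ages 2 to 21; I assume 0.5 to 2.0 m².

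- Reduction: 4.5 - 3.8 = 0.7 mg/m², or 0.7 × BSA in mg.
- The step exceeds the reduction when 2 > 0.7 × BSA, that is, BSA < 2/0.7 = 2.86 m². This covers the whole assumed range.

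| BSA (m²) | Level 0 (mg) | Level -1 (mg) | Level -1 plus 2 mg | Rounded to whole mg |
|---|---|---|---|---|
| 0.8 | 3.60 | 3.04 | 5.04 | 4 → 3 → 5 |
| 1.3 | 5.85 | 4.94 | 6.94 | 6 → 5 → 7 |
| 2.0 | 9.00 | 7.60 | 9.60 | 9 → 8 → 10 |

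Three conditions apply to every row: the trough on the reduced dose is below 5 ng/mL, the site aims at the range as 5.2.4 says, and it takes the 2 mg step from 4.5.1.2. The last column also assumes rounding of later doses; section 4.3.2 states rounding only for the initial dose.

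**3. Reaching the floor through toxicity reductions**

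With the same rounding, a dose becomes 2 mg when level × BSA < 2.5 mg:

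- Level 0: 2.5/4.5 = 0.56 m²
- Level -1: 2.5/3.8 = 0.66 m²
- Level -2: 2.5/3.0 = 0.83 m²

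So 2 mg is reached after one reduction at about 0.56–0.66 m² and after two at about 0.66–0.83 m². The conflict then needs a further recurrence. Section 7.6 stops the trial above 30%, giving 4 of the first 10 as an example: 3/10 = 30% does not cross it and 4/10 = 40% does, so one child's classification could matter.

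**4. The two step rules**

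Unrounded, they coincide at 2/0.33 = 6.06 mg for increases and 2/0.25 = 8 mg for decreases. Rounded to whole milligrams:

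| Dose (mg) | +2 mg | +33% | -2 mg | -25% |
|---|---|---|---|---|
| 3 | 5 | 3.99 (4) | 1 (floor 2) | 2.25 (2) |
| 4 | 6 | 5.32 (5) | 2 | 3.00 (3) |
| 5 | 7 | 6.65 (7) | 3 | 3.75 (4) |
| 6 | 8 | 7.98 (8) | 4 | 4.50 (tie) |
| 7 | 9 | 9.31 (9) | 5 | 5.25 (5) |
| 8 | 10 | 10.64 (11) | 6 | 6.00 (6) |
| 9 | 11 | 11.97 (12) | 7 | 6.75 (7) |

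At 2 mg the increases also differ: 4 mg against 2.66 (3) mg. Upward differences therefore occur at 2–4 mg and again at 8 and 9 mg, so they are not confined to small children.

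**The case against.** The strongest reply is that a specific rule governs a general one: 4.5.1.2 addresses toxicity by name, 5.2.4 is a monitoring schedule, and titration is subject to tolerability throughout. That is a reasonable reading, but the protocol states no such order of precedence, and the tolerability qualifier does not say that targeting ends after a toxicity reduction.

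A reader might infer that 5.2.4 alone sends the child up by 2 mg. It does not. It gives no step size; the 2 mg step comes from 4.5.1.2, the section that holds the exclusion, so a site would have to use one bullet and overlook another. The figures above are therefore conditional. A reader might also infer a breach of the 5 mg/m² per day that section 1.4 cites as the paediatric maximum tolerated dose. The documents do not support using that as a ceiling, because 4.5.1.2 itself lists levels of 5.2 and 6 mg/m².

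On the floor, the alternate-day bullet follows the trough bullets, so it can be read as trough-driven only. Its text sets no such limit, and 4.6.2 mentions alternate-day dosing to manage toxicity, though only for patients on moderate inhibitors. The point stands in reduced form.

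On step size, calling the rules a flat contradiction would go too far. The percentages sit under the interaction heading and most naturally apply to patients on interacting drugs, whose use of strong inhibitors or inducers is to be discussed with the study PI or chair. What remains is that 4.5.1.1 brings the same patients into general monitoring and 4.5.1.2 does not exempt them from the 2 mg step.

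**Conclusion.** The main point holds and should be fixed. Sections 4.5.1.2 and 5.2.4 give opposite instructions on trough targeting after a toxicity adjustment, and the schedule sends sites to the one without the exception. This rests on the text alone. The sizing, in which one 2 mg step outweighs one level of reduction below 2.86 m², rests on an assumed BSA, a trough below 5 ng/mL on the reduced dose, and use of the 4.5.1.2 step. The documents give no basis for saying how often that would occur.

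The floor point is secondary. It is limited to recurrent grade 3 toxicity or recurrent intolerable grade 2 mucositis at 2 mg daily, and it bears on section 7.6 only through how such a child is classified. The step-rule overlap and the undefined increment are minor questions of scope.

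None of this shows that either side of any of these pairs is the correct clinical rule.

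**What to change.** The sponsor should reconcile three sets of passages:

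- **4.5.1.2 and 5.2.4:** state whether trough targeting applies after an adjustment for toxicity, in the same terms in both places. Footnote 9 of Appendix II and section 5.2.1 should point to the reconciled text.
- **4.5.1.2 and the recurrence rows of Tables 4-1 and 4-2:** state what triggers the alternate-day bullet and give one action for recurrent toxicity at 2 mg daily, so that the section 7.6 count is unambiguous.
- **4.5.1.2 and 4.6.2:** state which patients each trough step rule covers, and define the increment.

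The content of each rule is the sponsor's clinical decision; none is proposed here. The cost is protocol amendment wording and a memo to sites, with no added visits, procedures or patients.

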AST or ALT elevation Grade 4 (> 20 x ULN)*	Interrupt Everolimus administration until resolution to ≤ grade 1 (or ≤ grade 2 if baseline values were within the range of grade 2). If resolution occurs ≤ 7 days, Everolimus should be re-started at one dose level lower. If resolution takes > 7 days, discontinue Everolimus.
Recurrence of Grade 4 AST or ALT elevation after dose reduction or toxicity requiring Everolimus interruption for > 28 days	Discontinue Everolimus.
Intolerable grade 2 mucositis, or grade 3 AE, except hyperglycemia or hypertriglyceridemia or hypercholesterolemia	Interrupt Everolimus administration until resolution to ≤ grade 1 or baseline grade / value. If resolution occurs within ≤ 7 days, Everolimus should be re-started at the dose level prior to interruption. If resolution takes > 7 days, or if event recurs within 28 days, hold Everolimus until recovery to ≤ grade 1 or baseline grade / value and reintroduce Everolimus at one dose level lower, if available. Patients will be withdrawn from the study if they fail to recover to ≤ grade 1 or baseline grade / value within 28 days.
Any other grade 4	Hold Everolimus until recovery to grade ≤ 1 or baseline value Reintroduce Everolimus at one dose level lower, if available.
Grade 3 or 4 clinical liver failure (asterixis or encephalopathy/coma)	Discontinue Everolimus
Recurrence of intolerable grade 2 mucositis or grade 3 event after dose reduction	Reduce dose to the next lower dose level, if available. The lowest possible dose level of Everolimus is 2 mg daily. Below this level, Everolimus must be discontinued.
Recurrence of grade 4 after dose reduction	Discontinue Everolimus
Any non-hematologic toxicity requiring Everolimus interruption for > 28 days	Discontinue Everolimus

* Should HCV flare be confirmed, the guidelines for flare must take precedence (Table 4-4).

Table 4-2**Dosing guidelines for Everolimus-related hematologic toxicities**

Toxicity	Action
Grade 2 thrombocytopenia (platelets <75, \geq 50x109/L)	Interrupt Everolimus until resolution to grade \leq 1 If resolution occurs \leq 7 days, reintroduce Everolimus at the dose level prior to interruption. If resolution occurs $>$ 7 days, or event occurs within 28 days, reintroduce Everolimus at one dose level lower, if available.

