Grade 3 thrombocytopenia (platelets <50, \geq 25 x109/L)	Interrupt Everolimus until resolution to grade \leq 1 If resolution occurs \leq 7 days, reintroduce Everolimus at the dose level prior to interruption. If resolution occurs $>$ 7 days, or event occurs within 28 days, reintroduce Everolimus at one dose level lower, if available.
Grade 4 thrombocytopenia (platelets < 25 x109/L)	Interrupt Everolimus until recovery to grade \leq 1. Then reintroduce Everolimus at one dose level lower, if available.
Grade 3 neutropenia or anemia (neutrophil <1, \geq 0.5 x109/L)	Interrupt Everolimus until resolution to grade \leq 2 or baseline value If AE resolution occurs \leq 7 days, reintroduce Everolimus at the same dose level. If AE resolution occurs $>$ 7 days, or event occurs within 28 days, reintroduce Everolimus at one dose level lower, if available.
Grade 4 neutropenia or anemia	Interrupt Everolimus until recovery to grade \leq 2 or baseline value. Reintroduce Everolimus at one dose level lower, if available.*
Grade 3 febrile neutropenia	Interrupt Everolimus until resolution to grade \leq 1 (or baseline value) and no fever. Reintroduce Everolimus at one dose level lower, if available.*
Grade 4 febrile neutropenia	Discontinue treatment
Recurrence of grade 3 toxicity after dose reduction	Reduce dose to the next lower dose level, if available. The lowest possible dose level of Everolimus is 2 mg daily. Below this level, Everolimus must be discontinued.
*Recurrence of grade 4 toxicity (including febrile neutropenia) after dose reduction	Discontinue Everolimus
*Any hematologic toxicity requiring Everolimus interruption for $>$ 28 days	Discontinue Everolimus

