7.6 Stopping Rules

Occurrence of >30% of patients requiring permanent discontinuation of Everolimus in this study (i.e., 4 of the first 10 patients or 6 of the first 16 patients) will lead to stopping this study. A minimum of six patients will be treated.

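### The toxicity dose ladder ends at Level -2 (3 mg/m²), but the lowest dose level is also given as 2 mg daily, so the action on recurrent grade 3 toxicity at Level -2 is undefined above a BSA of about 0.83 m²

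*Combined protocol and SAP*

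**What the plan says.** All references are to the combined protocol and SAP.

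- **The ladder (Section 4.5.1.2).** For patients who do not tolerate the schedule, five levels are given per m². The lower three are "Level -2 = 3 mg/m²/dose, Level -1 = 3.8 mg/m²/dose, Level 0 = 4.5 mg/m²/dose"; the upper two are 5.2 and 6 mg/m². There is no level below -2.
- **The flat floor (same list).** "The lowest possible dose level of Everolimus is 2 mg daily". This is a fixed amount, not scaled to body size.
- **Table 4-1, recurrence row.** If grade 2 mucositis that the patient cannot tolerate, or a grade 3 event, returns once the dose has been reduced, the instruction is "Reduce dose to the next lower dose level, if available. The lowest possible dose level of Everolimus is 2 mg daily". It continues: "Below this level, Everolimus must be discontinued".
- **Table 4-2, recurrence row.** Recurrent grade 3 hematologic toxicity is handled the same way: "The lowest possible dose level of Everolimus is 2 mg daily. Below this level, Everolimus must be discontinued".
- **Table 4-5.** For hepatitis B reactivation only, a patient already on the protocol's lowest dose restarts at the same dose. The table does not say which lowest dose it means.
- **Section 7.6.** The study stops on "Occurrence of >30% of patients requiring permanent discontinuation of Everolimus in this study", illustrated as 4 of the first 10 patients or 6 of the first 16.

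**The concern.** Both bottoms are called a dose level, and the recurrence rows tell the site to move to the next lower one if there is one. On the mg/m² ladder nothing lies below Level -2. On the flat scale a child taking more than 2 mg still has room to go down and has not reached the point at which discontinuation is required. The reader cannot tell which scale governs.

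The question arises for a child who has already been reduced to Level -2 for toxicity and then has another qualifying event. Different answers mean different exposure after repeated toxicity. They also decide whether the child is counted as permanently discontinued under Section 7.6. The trial is multi-center, so one event could be handled differently from site to site.

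**Working it through.** The plan states no derived figure here, so there is none to reproduce. The check asks where the two bottoms coincide, then applies the recurrence rows where they do not.

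**Inputs**
- Level -2 = 3 mg/m² and floor = 2 mg daily (Section 4.5.1.2).
- Tablets of 2, 3 and 5 mg (Section 4.3.3). These make every whole-milligram dose from 2 mg up: 2, 3, 2+2, 5, 3+3, 2+5, and so on.
- Rounding to the nearest dose the tablets allow (Section 4.3.2). That section covers the initial calculated dose; applying it to reduced doses is an assumption.
- BSA is not given. Ages run from 2 to 21 years (Section 3.1.1). A range of 0.5 to 2.0 m² is assumed for illustration.

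**Step 1: where the bottoms coincide**
- Unrounded: 3 × BSA = 2, so BSA = 2/3 = 0.67 m².
- Rounded: Level -2 gives 2 mg while 3 × BSA is below 2.5, so up to BSA = 2.5/3 = 0.83 m².

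**Step 2: the gap above that point**

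| BSA (m²) | 3 × BSA (mg) | Level -2, rounded (mg) | Flat floor (mg) | Gap (mg) |
|---|---|---|---|---|
| 0.8 | 2.4 | 2 | 2 | 0 |
| 0.84 | 2.52 | 3 | 2 | 1 |
| 1.0 | 3.0 | 3 | 2 | 1 |
| 1.3 | 3.9 | 4 | 2 | 2 |
| 1.6 | 4.8 | 5 | 2 | 3 |
| 1.8 | 5.4 | 5 | 2 | 3 |
| 2.0 | 6.0 | 6 | 2 | 4 |

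Tablet strength therefore does not settle whether a lower level is available: in every row with a gap, a smaller dose can be dispensed.

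**Step 3: applying the recurrence rows to a child at Level -2 taking more than 2 mg**

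Once the required interruption has ended in recovery, three readings fit the text:
1. *Restart at the same dose.* The ladder has no lower level, and the child is not below 2 mg.
2. *Reduce toward 2 mg.* The lowest dose level is 2 mg, so room remains. No step size is given for this; the 2 mg steps in Section 4.5.1.2 serve trough titration, and the same section takes doses adjusted for toxicity out of trough targeting.
3. *Stop.* Level -2 is the bottom of the toxicity ladder, and the tables discontinue below the lowest level.

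**Step 4: link to Section 7.6**

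The threshold is more than 30%. Among the first 10 patients, 3/10 = 30% does not cross it and 4/10 = 40% does. One child's classification could decide the matter. How likely that is cannot be worked out from the documents.

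At or below about 0.83 m² the rounded Level -2 dose is already 2 mg, and this gap does not arise. A different question arises there, because Section 4.5.1.2 also says "If dose reduction is required for patients receiving the lowest available strength, administer every other day" while the tables discontinue. The present point does not rely on it.

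**The case against.** The strongest defense is that the two bottoms are compatible. The 2 mg line follows the trough-titration steps and matches the smallest tablet. A tablet floor beneath a BSA ladder does real work: at 0.5 m², Level -2 is 1.5 mg, which cannot be dispensed. On that reading a gap of some milligrams between floor and ladder is expected and measures no harm. This is a fair reading, and it narrows the defect. It does not remove it, because the action at Level -2 above 2 mg is still not stated.

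A reader might infer that a child could simply be kept on an unchanged dose through continuing grade 3 toxicity. The documents do not support that. The general grade 3 row of Table 4-1 (which excepts hyperglycemia and raised lipids) requires interruption until recovery, as does its grade 3 AST/ALT row. Table 4-2 does the same for grade 3 thrombocytopenia, neutropenia and anemia. Both tables discontinue when an interruption exceeds 28 days. Nothing says the recurrence rows cancel these holds. The most the text allows is a restart at the same dose after recovery.

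There are also general backstops. Sections 4.5 and 4.8 end treatment for unacceptable toxicity, and Section 5.5 allows removal when continuing is unsafe or against the patient's interest. These stand as protection, but they permit stopping without saying which of the three actions applies.

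A reader might also infer that most children are affected. No age or BSA distribution is given. With BSA spread evenly from 0.5 m², the share above 0.83 m² is (1.0 − 0.833)/0.5 = 33% if the upper limit is 1.0 m², 52% if it is 1.2 m², 72% if it is 1.7 m² and 78% if it is 2.0 m². The share depends wholly on the assumption.

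Finally, the situation needs a child at Level -2 with a further qualifying event, in an 18-patient trial, and its frequency is unknown.

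**Conclusion.** The concern holds as an internal inconsistency in the dose-modification rules; it is not a design choice. Section 4.5.1.2 and Tables 4-1 and 4-2 use one term for two different bottoms. For a child at Level -2 with BSA above about 0.83 m², they leave open whether to restart unchanged, reduce further or stop once a recurrent grade 3 event has resolved. Within the assumed BSA range the two bottoms differ by 1 to 4 mg in such children.

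The 0.83 m² crossover assumes that nearest-milligram rounding extends to reduced doses; without rounding it is 0.67 m². The share of children above either value is not known.

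The choice of reading can affect safety and the Section 7.6 count, but the size of that effect cannot be estimated from the documents. A reader might go further and infer damage to the primary endpoint, since an early stop could keep a child from being documented with six months of stable disease. That is possible, but nothing in the documents shows how often it would occur, so the point does not rest on it.

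**What to change.** Reconcile the dose-level list in Section 4.5.1.2, the recurrence rows of Tables 4-1 and 4-2, and the reference in Table 4-5 to the protocol's lowest dose. Two things need to be stated:

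1. Either one lowest dose level in one unit, used throughout, or an explicit relation between the mg/m² ladder and the 2 mg floor.
2. A single action for a child at that level whose grade 3 toxicity recurs, after the interruption and recovery already required.

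The sponsor's clinicians choose the level and the action; this review takes no view on either. Section 7.6 needs no change for this point: if the stated action is to stop for good, it counts there on the rule's plain words.

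The cost is a wording amendment with IRB approval under Section 10.7. Sample size, assessments and analysis methods are unaffected.
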